  LSMEANS TRT TRT*ATPTN /DIFF ALPHA=0.1 CL;  
RUN;
```

In the above statements:

- TRT represents the treatment (active or placebo);
- ATPTN represents the postdose nominal time point;
- BASE represents the baseline value for QTcF;
- CONC represents measured plasma concentrations of moxidectin;

- SP(POW) is a spatial power law covariance structure (a time-dependent first-order autoregressive covariance designed for unequally-spaced time points), if the model does not converge then unstructured or compound symmetry structures will be assessed, in that order;
- LSMEAN differences between the treatments at the Geometric C_{\max} value and at the average concentration value, where xx.x represents the largest geometric mean C_{\max} value among the doses, most likely for the 36-mg dose, will be provided.

Model assumptions will be reviewed with plots of standardized residuals versus fitted values and normal Q-Q plots of the standardized residuals. If nonlinearity is present, a log linear and/or maximum effect (E_{\max}) or other model will be considered.

Similar analyses will be repeated for HR, PR, and QRS, however, bootstrap percentiles will be based on the 2.5th and 97.5th percentiles, corresponding to a 2-sided 95% CI rather than the 2-sided 90% CI.

Secondary Analysis: Pharmacokinetic/Pharmacodynamic Analyses

To evaluate the relationship between placebo-corrected mean change from Baseline in QTcF (ie, ddQTcF) versus plasma concentrations of moxidectin for all subjects in the PK/PD population, both graphical and mixed-effects analyses of plasma concentration of ddQTcF versus plasma concentration of moxidectin will be performed. The mixed-effects model will be used to account for the clustering effects within each subject at different time points. The mixed-effects model will contain ddQTcF as the dependent variable and include the corresponding time-matched plasma moxidectin concentrations as the independent variable. The mixed-effects model will be used to estimate, for all subjects, the predicted population mean ddQTcF and its corresponding upper 95% 1-sided (equivalent to the upper 90% 2-sided) CI over a range of observed plasma concentrations. A negative result (ie, the model indicates no plasma concentration effect) is a slope of approximately zero.

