The adequacy of the linear assumption between ddQTcF and plasma concentrations will be determined by adding a quadratic term to the mixed-effects model. If the quadratic term is different than zero, having $P < 0.05$, and Akaike's information criterion (AIC) is smaller in comparison with the linear model's AIC, then a quadratic term may be added. In addition, a transformation of the concentrations (eg, $\log[C/LLOQ]$, where LLOQ is the lower limit of quantitation of the assay and all values below the LLOQ are replaced with the LLOQ) may also be assessed. The best model fit will be determined by the lowest AIC.

The predicted mean expected ddQTcF and the 90% 2-sided CI will be calculated using the estimates of the slopes from the mixed-effect models, for all subjects, at relevant concentration levels (ie, the mean maximum plasma concentration under each dose level).

The relevant SAS code statements are:

```
PROC MIXED DATA = DATA;  
  CLASS SUBJID;  
  MODEL ddQTcF = CONC /SOLUTION OUTPM=PRED ALPHA=0.05;  
  RANDOM INTERCEPT CONC / TYPE=UN SUBJECT = SUBJID;  
RUN;
```

In the above statements:

- CONC represents the measured plasma concentrations of moxidectin;
- Type=UN means an unstructured covariance matrix, which is used for the correlated random effects (INTERCEPT and CONC). If the model does not converge other covariance structures will be investigated.

A plot will be provided to show CI of each treatment using the following model, adding in the treatment variable as follows:

```
PROC MIXED DATA = DATA;  
  CLASS SUBJID TRT;  
  MODEL ddQTcF = CONC TRT/SOLUTION OUTP=PRED;  
  RANDOM INTERCEPT CONC /TYPE=UN SUBJECT = SUBJID;  
RUN;
```

Where TRT represents the individual treatments (moxidectin 4 mg, moxidectin 8 mg, moxidectin 16 mg, moxidectin 24 mg, and moxidectin 36 mg).

A plot of the observed median-decile drug concentrations and associated mean ddQTcF (90% CI) together with the mean model-predicted ddQTcF will be used to evaluate the adequacy of the model fit to the assumption of linearity and the impact on quantifying the concentration response relationship.

Categorical QTc Findings

Categorical summaries using the largest postdose QTcF and largest change from Baseline (dQTcF) will be performed to determine the number and percentage of subjects, by treatment, who meet each of the following criteria:

- Result ≤ 450 msec;
- Result > 450 and ≤ 480 msec;
- Result > 480 and ≤ 500 msec;
- Result > 500 msec;
- dQTcF ≤ 30 msec;

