14.2 Pharmacokinetic and Pharmacodynamic Summary Tables

14.2.1 Concentration and Pharmacokinetic Summaries, Analyses, and Figures

Table 14.2.1.1	Summary of Plasma Concentrations Over Time (PK Population)
Table 14.2.1.2	Summary of Plasma Pharmacokinetic Parameters (PK Population)
Table 14.2.1.3	Summary of Urine Pharmacokinetic Parameters (PK Population)
Table 14.2.1.4	Summary of Feces Pharmacokinetic Parameters (PK Population)
Figure 14.2.1.1	Mean \pm SD Plasma Moxidectin Concentration (ng/mL)-Time Profile, Linear Scale (PK Population)
Figure 14.2.1.2	Mean Plasma Moxidectin Concentration (ng/mL)-Time Profile, Semilogarithmic Scale (PK Population)
Figure 14.2.1.3	Mean \pm SD Plasma Moxidectin Metabolite Concentration (ng/mL)-Time Profile, Linear Scale (PK Population)
Figure 14.2.1.4	Mean Plasma Moxidectin Metabolite Concentration (ng/mL)-Time Profile, Semilogarithmic Scale (PK Population)
Figure 14.2.1.5	Mean \pm SD Plasma Moxidectin Metabolite to Parent (molar equivalents) Ratios Over Time (PK Population)
Figure 14.2.1.6	Mean \pm SD Urine Moxidectin Amount Excreted Over Time (PK Population)
Figure 14.2.1.7	Mean \pm SD Urine Moxidectin Metabolite Amount Excreted Over Time (PK Population)
Figure 14.2.1.8	Mean \pm SD Urine Moxidectin Metabolite to Parent Amount Excreted (molar equivalents) Ratios Over Time (PK Population)
Figure 14.2.1.9	Mean \pm SD Feces Moxidectin Amount Excreted Over Time (PK Population)

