14.2.2 Pharmacodynamic Summaries, Analyses, and Figures

Table 14.2.2.1	Summary of Continuous ECG Parameter Results and Change From Baseline (ECG Population)
Table 14.2.2.2	Summary of Simple/Unadjusted Continuous ECG Parameters (ECG Population)
Table 14.2.2.3	Summary of Primary Analysis Mixed-Effects Model Parameters (ECG Population)

Table 14.2.2.4	Summary of Primary Analysis Mixed-Effects Model Predicted ddECG and Predicted Interval at Geometric Mean Maximum Plasma Concentration (ECG Population)
Table 14.2.2.5	Summary of Secondary Analyses Mixed-Effects Model Predicted Regression Slope Estimates and Predictions (PK/PD Population)
Table 14.2.2.6	Summary of Continuous QTcF Interval Categories (ECG Population)
Table 14.2.2.7	Summary of Continuous PR, QRS, and HR Outliers (ECG Population)
Table 14.2.2.8	Summary of Continuous ECG Diagnostic Statements (ECG Population)
Table 14.2.2.9	Summary of Treatment-Emergent Continuous ECG Diagnostic Statements (ECG Population)
Figure 14.2.2.1	dQTcF Interval vs. Time Showing Mean and 2-sided 90% Confidence Bounds (ECG Population)
Figure 14.2.2.2	dHR vs. Time Showing Mean and 2-sided 95% Confidence Bounds (ECG Population)
Figure 14.2.2.3	dPR Interval vs. Time Showing Mean and 2-sided 95% Confidence Bounds (ECG Population)
Figure 14.2.2.4	dQRS Interval vs. Time Showing Mean and 2-sided 95% Confidence Bounds (ECG Population)
Figure 14.2.2.5	dRR Interval vs. Time Showing Mean and 2-sided 95% Confidence Bounds (ECG Population)
Figure 14.2.2.6	ddQTcF Interval vs. Time Showing Mean and 2-sided 90% Confidence Bounds (ECG Population)
Figure 14.2.2.7	ddHR vs. Time Showing Mean and 2-sided 95% Confidence Bounds (ECG Population)
Figure 14.2.2.8	ddPR Interval vs. Time Showing Mean and 2-sided 95% Confidence Bounds (ECG Population)
Figure 14.2.2.9	ddQRS Interval vs. Time Showing Mean and 2-sided 95% Confidence Bounds (ECG Population)
Figure 14.2.2.10	ddRR Interval vs. Time Showing Mean and 2-sided 95% Confidence Bounds (ECG Population)
Figure 14.2.2.11	Residual Plots From Primary Analyses by Parameter (ECG Population)
Figure 14.2.2.12	ddQTcF Interval vs. Plasma Moxidectin Concentrations (PK/PD Population)
Figure 14.2.2.13	ddQTcF Interval vs. Plasma Moxidectin Concentration by Treatment (PK/PD Population)
Figure 14.2.2.14	Observed Median-decile Plasma Moxidectin Concentrations and Associated Mean ddQTcF Interval (90% CI) Together With the Mean (90% CI) Predicted ddQTcF Interval (PK/PD Population)

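### The secondary ddQTcF code gives 95% limits where the text requires 90%, and as printed it compares models with different fixed effects by REML-based AIC

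*SAP*

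**What the plan says.** All of this concerns the secondary PK/PD analysis in SAP section 8.3.

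- **Confidence level in the text.** Over the observed concentration range the model is to give the predicted mean ddQTcF and its "corresponding upper 95% 1-sided (equivalent to the upper 90% 2-sided) CI over a range of observed plasma concentrations". At the mean maximum concentration of each dose: "The predicted mean expected ddQTcF and the 90% 2-sided CI will be calculated using the estimates of the slopes". Appendix A, Figure 14.2.2.14, carries the same level: "Together With the Mean (90% CI) Predicted ddQTcF Interval".
- **Confidence level in the code.** The main secondary model is "MODEL ddQTcF = CONC /SOLUTION OUTPM=PRED ALPHA=0.05". The by-treatment plot model, "MODEL ddQTcF = CONC TRT/SOLUTION OUTP=PRED", sets no level. The LSMEANS statements of the primary model, by contrast, use ALPHA=0.1.
- **Model choice.** A quadratic term may be added if its P value is below 0.05 and AIC falls. A log(C/LLOQ) transformation may also be assessed. Then: "The best model fit will be determined by the lowest AIC". Neither secondary PROC MIXED call has a METHOD= option, and the text does not name an estimation method for the comparison.
- **Unit.** The Appendix A figures plan plasma concentration in ng/mL, for example "Mean Plasma Moxidectin Concentration (ng/mL)-Time Profile, Semilogarithmic Scale (PK Population".

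**The concern.** There are two separate faults in the same block of code.

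**Level.** SAS splits ALPHA= and ALPHAP= over two tails. An upper one-sided 95% limit therefore needs 0.1, not 0.05. A likely cause is that the one-sided 5% was carried straight into the option. The limits produced would not be at the level that the text and the figure title state.

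**Model choice.** The three candidates differ in their fixed effects. PROC MIXED uses REML unless told otherwise, and the REML likelihood contains log|X′V⁻¹X|, which depends on the scale of the regressors. Its AIC penalty counts only covariance parameters, of which there are 4 in each candidate, so the extra quadratic coefficient costs nothing. The chosen curve, and with it the predicted ddQTcF at each dose's mean Cmax, can then follow the scale of the regressor instead of the fit. The SAP gives this analysis a real task: section 8.3 explains that it guards against a spurious circadian slope in the primary dQTcF model.

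**Working it through.** **1. Confidence level**

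Inputs: 90% two-sided from the text, and an effective two-sided alpha of 0.05 from the code (ALPHAP= absent, software default). Limits are estimate ± quantile(1 − alpha/2) × SE.

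- The SAP's own equivalence reproduces: z for 90% two-sided = z for 95% one-sided = 1.645.
- As coded: z = 1.960.
- Ratio of half-widths: 1.960/1.645 = 1.19. With t on 48 df (an assumed df): 2.011/1.677 = 1.20.
- Upper limit too high by (1.960 − 1.645) × SE = 0.32 × SE, or (2.011 − 1.677) × SE = 0.33 × SE with t. For an assumed SE of 1 to 3 msec, the z version is 0.32 to 0.95 msec.

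**2. Unit dependence of REML AIC (exact, no assumptions)**

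−2 × REML log-likelihood includes +log|X′V⁻¹X|. Going from ng/mL to µg/mL multiplies CONC by 1/1000 and CONC² by 1/1000², and leaves log(C/LLOQ) unchanged.

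| Model | Change in REML AIC |
|---|---|
| Linear | −2 ln(1000) = −13.82 |
| Quadratic | −2 ln(1000) − 4 ln(1000) = −41.45 |
| Log | 0 |

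So AIC(quadratic) − AIC(linear) falls by 4 ln(1000) = 27.63, and AIC(log) − AIC(linear) rises by 2 ln(1000) = 13.82. Fitted values do not change.

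One simulated data set (50 active subjects × 14 postdose times, random intercept and slope, unstructured covariance, all inputs assumed) shows the effect:

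| Method, unit | Quadratic − linear | Log − linear |
|---|---|---|
| REML, ng/mL | +16.06 | −7.09 |
| REML, µg/mL | −11.57 | +6.73 |
| ML, either unit | +1.04 | +0.42 |

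Under REML the unit alone reverses both comparisons. Under ML nothing moves.

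**3. Size in the planned unit, ng/mL**

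The SAP gives no expected Cmax, variance or LLOQ. Assumed: top-dose Cmax 50, 100, 200 or 400 ng/mL; random-intercept SD 5 msec; residual SD 5, 7 or 9 msec; LLOQ 0.1 ng/mL. That makes 4 × 3 = 12 settings.

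- *Quadratic.* With the covariance parameters held fixed, adding the term changes REML AIC by −2 ln(SE_quad) − ln(2π) − t². AIC falls only if t² > −2 ln(SE_quad) − ln(2π).
  - SE_quad = 1.5×10⁻³ msec/(ng/mL)²: t² > 13.00 − 1.84 = 11.17, so |t| > 3.34 (P about 8×10⁻⁴).
  - SE_quad = 1.4×10⁻⁵: t² > 22.35 − 1.84 = 20.52, so |t| > 4.53 (P about 6×10⁻⁶).
  - The stated P < 0.05 condition is thus overridden by a far stricter one that depends on the unit.
- *Log versus linear.* The part of the AIC difference unrelated to fit is 2 ln(SE_lin/SE_log), which is −5.6 to −9.9 over these settings, in favour of log. No P-value condition guards this choice.
- *Illustration.* In one data set simulated with a truly linear relation and rescaled over the 12 settings, REML preferred log in all 12 (AIC difference −0.9 to −6.0), while ML preferred linear in all 12 (+3.8 to +4.9).

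**The case against.** **On the level.** The visible ALPHA=0.05 is not what sets the OUTPM limits, and without a CL option it may do nothing. The SAP's general alpha is 0.05 two-sided, and no 90% level is stated for the fixed effects. The calculation at each dose's mean Cmax has no printed code, so it is not shown to be wrong. The secondary result is judged by a slope near zero, not by these limits, and the error is conservative. Most of this is fair. It bears on which option to change, not on the result: the OUTPM limits are 95% with or without an effective ALPHA=, while the text asks for 90%.

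**On AIC.** The SAP never says that the comparison uses REML. The code is for the linear model only, the quadratic and log steps are optional, and a median-decile plot offers a further check. The µg/mL case is hypothetical, since ng/mL is planned, and one rescaled data set gives no selection rate. A small simulation (60 trials per setting, linear truth, residual SD 7 msec, other inputs assumed) found that REML chose log in 95–100% of trials for true effects of 0 to 3 msec at top Cmax, against 27–45% under ML. The two models' predictions there differed by only about 0.1 msec at no effect and 0.7 msec at 3 msec. At 6 msec (Cmax 50 ng/mL only), REML chose log in 43% and the gap was about 1.8 msec, with log lower.

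What stands is that the practical effect is modest and confined to a supportive analysis. It does not rescue the rule. Run as printed, the code gives REML AIC, the text makes lowest AIC decisive once the alternatives are assessed, and the bias is present in ng/mL itself.

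**Conclusion.** Both parts hold, and the plan is wrong as written.

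- **Level.** The OUTPM limits are 95% two-sided instead of 90%, with a half-width 1.19 to 1.20 times the stated one. The direction is conservative. This rests on the PROC MIXED default for ALPHAP=.
- **Selection.** Under the PROC MIXED default of REML, lowest AIC is not a valid way to choose among these models. The unit shifts of 27.63 and 13.82 are exact. The thresholds and the 5.6 to 9.9 advantage for log depend on the assumed Cmax and SD ranges, and the latter also on the assumed LLOQ. The simulations illustrate the fault and do not predict this trial's result.

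Neither part touches the primary bootstrapped criterion of 10 msec. The point should be corrected before the analysis is run, but it does not threaten the primary conclusion.

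**What to change.** 1. In the main secondary model keep OUTPM and add ALPHAP=0.1. Changing ALPHA= alone would leave the OUTPM limits at 95%. If fixed-effect limits are also wanted at 90%, set ALPHA=0.1 with CL.
2. For predictions at each dose's mean Cmax, print the code: ESTIMATE statements with CL ALPHA=0.1, or appended records at those concentrations with ddQTcF missing.
3. State the confidence level for the by-treatment plot, and use OUTPM there instead of OUTP if population-level limits are meant.
4. Add one sentence: linear, quadratic and log-concentration models are compared by AIC from METHOD=ML fits, and the chosen model is refitted by REML for estimates and limits.

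The cost is a few code options and one sentence in the SAP, with no change to data or design.

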3.2 Sample Size Considerations

The sample size of 60 subjects (10 subjects each in 6 treatment groups) is considered adequate to explore the effects of moxidectin on the corrected QT interval (QTc), as this design will yield 900 QTc-PK pairs in total. Additional subjects may be enrolled as alternates in this study should a subject choose to withdraw consent before study drug administration. Alternate subjects will remain in the clinical research unit (CRU) from Check-in until all subjects due to be dosed have completed dosing. Subjects who withdraw after dosing will not be replaced.

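### The SAS step listed for the by-treatment ddQTcF plot yields subject-specific 95% bands, not the 90% confidence interval of each treatment mean, and the companion step also writes 95% limits

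*SAP*

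**What the plan says.** All of this is in SAP Section 8.3, under the secondary pharmacokinetic/pharmacodynamic analyses, unless noted.

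- **Target.** The model is to give the "predicted population mean ddQTcF and its corresponding upper 95% 1-sided (equivalent to the upper 90% 2-sided) CI over a range of observed plasma concentrations". Section 8.2 also sets 90% as the level for QTcF intervals.
- **Companion (all-subjects) step.** "MODEL ddQTcF = CONC /SOLUTION OUTPM=PRED ALPHA=0.05", with random intercept and slope by subject.
- **By-treatment step.** Introduced with "A plot will be provided to show CI of each treatment using the following model". Its model statement is "MODEL ddQTcF = CONC TRT/SOLUTION OUTP=PRED" and its random statement is "RANDOM INTERCEPT CONC / TYPE=UN SUBJECT = SUBJID". It lists no `OUTPM=`, `LSMEANS`, `ESTIMATE` or `ALPHA=`.
- **Treatments.** "Where TRT represents the individual treatments (moxidectin 4 mg, moxidectin 8 mg, moxidectin 16 mg, moxidectin 24 mg, and moxidectin 36 mg", so five active doses. Section 3.2 gives the group size: "The sample size of 60 subjects (10 subjects each in 6 treatment groups").
- **Evident destination.** Figure 14.2.2.13 in Appendix A, ddQTcF against plasma concentration by treatment in the PK/PD population.

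**The concern.** The text and the code describe different quantities. A confidence interval for a treatment concerns the mean response at that dose. In PROC MIXED, `OUTPM=` gives that mean (fixed effects only) with its limits. `OUTP=` gives the prediction for a particular subject, including his predicted random intercept and slope. Because the model has subject-level random effects, the two differ in both centre and standard error. The plan itself uses `OUTPM=` one step earlier, where the stated target is the population mean, and gives no reason for the switch.

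The confidence level is a second mismatch. The by-treatment step takes the 95% default, and the companion step asks for 95% explicitly, while the text wants 90% two-sided limits. The plan equates 90% two-sided with 95% one-sided, which may be how 0.05 entered the code. But `ALPHA=0.05` produces two-sided 95% limits, so the upper limit is a 97.5% one-sided bound.

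At stake is a planned figure in which subject predictions could be presented as treatment confidence intervals, and secondary prediction limits at a level other than the one stated.

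**Working it through.** The SAP states no figure on this point to reproduce. The check has two parts: what the code outputs, and how far that lies from what the text asks for.

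**1. Code against text**

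| Step | Listed output with limits | Quantity | Level as coded | Level in text |
|---|---|---|---|---|
| Primary (dQTcF) | `LSMEANS ... ALPHA=0.1 CL` (`OUTP=` also listed, alongside `RESIDUAL`) | treatment means and differences | 90% | 90% (by bootstrap) |
| Secondary, all subjects | `OUTPM=PRED ALPHA=0.05` | x'b, population mean | 95% | 90% |
| Secondary, by treatment | `OUTP=PRED`, no `ALPHA=` | x'b + z'u, one subject | 95% (default) | 90% |

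`SOLUTION` prints coefficients, not limits for the mean along the concentration axis. In the by-treatment step, therefore, `OUTP=PRED` is the only listed source of a band.

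**2. Effect of the confidence level alone**

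Ratio of normal multipliers: 1.960 / 1.645 = 1.19. Limits at 95% are about 19% wider than limits at 90%. This applies to both secondary steps and needs no assumption about variances.

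**3. Effect of `OUTP=` instead of `OUTPM=`**

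Inputs from the SAP: 5 active doses, 10 subjects each, 14 postdose times (Section 8.1), and the model with CONC, TRT, and random intercept and slope.

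Assumed, because the SAP gives none:
- intercept SD 4 to 10 msec;
- slope SD 3 to 5 msec per unit of concentration, scaled to roughly the top-dose peak;
- residual SD 6 to 9 msec;
- a dose-proportional concentration profile;
- uncorrelated random effects (the SAP allows correlation) and known variance components.

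Method: solve the mixed-model equations for this design. Take the standard error of x'b (`OUTPM=`) and of x'b + z'u (`OUTP=`) at each record. Then compare the centres and count the 95% `OUTP=` intervals that miss the fitted mean of their own dose at the same concentration. Centres and counts come from one simulated data set per setting.

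Results at 36 mg (msec):

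| SDs: intercept / slope / residual | SE of mean | 90% half-width wanted (1.645 × SE) | SE of subject prediction | 95% half-width as listed (1.960 × SE) | Shift of centre from mean line | Bands missing the mean |
|---|---|---|---|---|---|---|
| 4 / 3 / 6 | 1.55 | 2.55 | 1.71 | 3.35 | −4.6 to 5.0 | 44% |
| 6 / 4 / 6 | 2.15 | 3.54 | 1.82 | 3.57 | −6.8 to 8.4 | 49% |
| 8 / 5 / 6 | 2.78 | 4.57 | 1.90 | 3.72 | −10.0 to 12.1 | 51% |
| 8 / 5 / 9 | 2.89 | 4.75 | 2.65 | 5.19 | −8.7 to 10.7 | 46% |
| 10 / 5 / 6 | 3.36 | 5.53 | 1.91 | 3.74 | −13.4 to 15.8 | 53% |

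Across all doses and settings, the ratio of the `OUTP=` to the `OUTPM=` standard error runs from about 0.5 (1.60 / 3.21, 4 mg, intercept SD 10) to about 1.1 (1.51 / 1.37, 4 mg, intercept SD 4). Between 20% and 80% of the 95% subject bands exclude their own treatment's fitted mean.

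The reason is plain. The standard error of a dose mean is driven by between-subject spread over 10 subjects. That of a subject's own prediction is driven mainly by residual noise over his 14 records. In the 6 / 4 / 6 row the two half-widths almost coincide (3.54 and 3.57), yet the bands still sit up to 8.4 msec from the mean line. Matching width would not make them intervals for the mean.

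**The case against.** The SAP says the plot uses a model; it does not say in words that the plot is drawn from the `PRED` data set. The code is offered as the relevant statements, the shells are in a separate document, and the primary step also writes `OUTP=` although its intervals come from elsewhere. `OUTP=` here may simply feed residual plots, which are planned for the secondary analysis (Figure 14.2.2.15). This stands in part: drawing the plot from `PRED` is the natural reading, not a stated commitment. But the primary step has `LSMEANS` statements and a bootstrap to supply its intervals. The by-treatment step has nothing else, so no listed statement produces the interval that the text describes.

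A reader might infer that each dose would be judged against 10 msec from the wrong error bars. The SAP does not support that. The 10 msec criterion is tied to the bootstrapped 90% interval of the primary dQTcF model at the largest geometric mean Cmax, and the figure carries no decision rule. Observed ddQTcF means with 90% intervals by dose and time point (Section 8.2, Figure 14.2.2.6) are also unaffected. And ten lines per dose would be hard to mistake for one treatment band.

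A reader might also infer that the error always narrows, or always widens, the bands. It does neither consistently, and the sizes above rest on assumed variance components.

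Finally, ddQTcF subtracts the placebo group's mean at each time point, and neither output option carries the sampling error of that mean (10 subjects). This is correct. It limits what even the corrected band can be called, which is why its label matters.

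**Conclusion.** The point holds as a mismatch between code and text in the supportive secondary analysis. As listed, the by-treatment step gives about ten subject-specific 95% bands per dose in place of one 90% confidence interval of the treatment mean. Which quantity `OUTP=` estimates does not depend on any assumption. How far the bands depart from the right one does: under the assumed variance components, standard errors are 0.5 to 1.1 times those of the mean, and centres lie several to about 20 msec away for the most extreme subjects. The 95% against 90% conflict affects both secondary steps and widens limits by about 19%.

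The reach is limited to what is evidently Figure 14.2.2.13 and, for the confidence level, the secondary model's prediction limits (Table 14.2.2.5 is their evident home). The primary analysis and its criterion for a negative QT assessment are untouched. It is worth correcting because it is free, not because it threatens the trial's main conclusion.

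**What to change.** In SAP Section 8.3, secondary analysis:

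- By-treatment step: replace `OUTP=PRED` with `OUTPM=PRED` and add `ALPHA=0.1`. If subject-level residuals are wanted for the residual plots, keep `OUTP=` as well, under a different data set name.
- Companion step: change `ALPHA=0.05` to `ALPHA=0.1`, so that both secondary models match the 90% two-sided interval in the text.
- State in the text and the figure footnote that the plotted band is the 90% confidence interval of the model-predicted treatment mean. It should not be described as a full interval for active minus placebo, since the placebo mean's sampling error is not in it.

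The cost is one keyword, two option values and a label. No data, design or primary analysis changes.
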